3.3.2.2 Vital Signs

Vital signs will be assessed during all study visits, including every day of the inpatient hospital stay (Cohort 1 subjects only). Vital signs measured will include blood pressure (BP, systolic and diastolic), HR, respiratory rate (RR), temperature (°C), and weight. Vital signs must be assessed following at least five minutes of rest (sitting) to ensure accurate measurement. No other measurements or procedures should be performed during this five-minute period. Vital signs will be collected prior to or after at least 30 minutes following the 6MWT. Vital signs should also be assessed in the case of abnormal clinical signs and symptoms. Height will be recorded at Screening.

3.3.2.3 12-Lead ECG

A 12-lead ECG will be recorded after at least five minutes rest in the semi-recumbent position at Baseline and repeated at Week 24/Premature Termination. Recordings should include lead II as a rhythm strip and contain at least five QRS complexes. The ECG parameters (after at least five minutes rest) include HR, PR interval, QT interval, QRS duration, and any clinically significant abnormalities.

3.3.2.4 Clinical Laboratory Assessments

The results of all clinical laboratory tests conducted at Screening and Baseline must be assessed by the Investigator to determine each subject's eligibility to participate in the study. Clinical laboratory results outside the normal reference range must be assessed and documented by the Investigator as to clinical significance. Clinically significant refers to a laboratory value that is unusual with respect to the subject's medical history or current health status.

Clinically significant abnormal laboratory test values will be treated and/or followed-up until the symptoms or values return to normal or acceptable levels, as judged by the Investigator. When appropriate, medical tests and examinations will be performed to document resolution of event(s).

3.3.2.4.1 Clinical Chemistry and Hematology

Blood and urine specimens for the measurement and evaluation of clinical chemistry and hematology will be collected at the Screening and Baseline visits prior to administration of oral treprostinil and repeated at the Week 12 and Week 24/Premature Termination to assess for study treatment-emergent changes in clinical chemistry and hematological laboratory parameters. Values for the following parameters will be obtained:

Electrolyte Panel

Chemistry Panel

•

•

•

Total bilirubin

Alkaline phosphatase

Alanine aminotransferase

- Sodium
- Potassium
- Bicarbonate
- Chloride
- Aspartate aminotransferase
- Urea nitrogen
- Creatinine
- Calcium
- Albumin

Hematology Panel

- Hemoglobin
- Hematocrit
- Red blood cell count
- Red blood cell morphology
- White blood cell count
- Platelet count

3.3.2.4.2 Pregnancy Testing

Females of childbearing potential include any female who has experienced menarche. Urine pregnancy tests (for all females of child-bearing potential) will be conducted at Screening, Baseline, and all subsequent study visits. A positive pregnancy test will exclude the subject from further participation in the study. Pregnant subjects who are discontinued from the study will be transitioned to an alternate therapy at the discretion of the Investigator.

3.3.2.5 Adverse Events

Adverse Events will be recorded throughout the course of the study from the time that each subject and/or caregiver signs the informed consent/assent form until the time screen failure is documented, or until the subject is either discontinued from the study or all Week 24 study assessments have been completed. Each subject/caregiver will be directly questioned for AEs at each scheduled study visit and during required telephone contacts. Subjects/caregivers will also be instructed to spontaneously report all AEs throughout the study. Additionally, a detailed collection of prostacyclin-related AEs will be captured via a standardized diary completed by the subject and/or caregiver each day of the five day inpatient hospital stay during the transition from IV/SC Remodulin to oral treprostinil or all subjects in Cohort 1.

All AEs should be followed until either resolution (or return to normal or baseline values), until they are judged by the Investigator to no longer be clinically significant, or for at least 30 days if the AE extends beyond the final study visit. All AEs meeting the criteria for serious (i.e., serious adverse events [SAEs]) should be followed until resolution, death, or the subject is lost to follow-up even if they are ongoing more than 30 days after completion of the final study visit.

All AEs/SAEs that occur while the subject is on oral treprostinil will be recorded as instructed in this protocol (Section 9.3).

If, at any time, the subject withdraws from the study and/or changes from study drug to commercially available Orenitram, any AEs/SAEs that occur on Orenitram (including product use errors, product quality problems, and therapeutic failures) will be reported following local post-marketing reporting requirements. These events will not be included in the eCRF.

Pulmonary arterial hypertension symptoms (Section 3.3.1.4) and PAH disease related events (Section 9.1.4) should only be recorded as an AE if the event is serious, new, or unusual with respect to intensity, frequency, or duration as compared to symptoms in the subject's medical history; or there is a reasonable possibility that the event was caused by the study drug.

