- ⁿ The maximum time to titrate off IV/SC Remodulin is four weeks from the start of the transition; if the subject is not fully transitioned by Week 4, they will be removed from the study. Subjects do not need to return to clinic for a visit at Week 4.
- ^o Daily telephone contact (excluding weekends and inpatient hospital stay) is required for the first two weeks of the study. Weekly telephone contact is required from the Week 3 visit until the Week 12 visit and then at least every other week until the Week 24 visit. Subjects may be contacted via email in lieu of a telephone call. A copy of the emails and/or telephone contact sheets must be documented in the subject's source documentation. Email should not replace direct follow-up by phone or in clinic for clinical significant AEs or other emergent issues.
- P All AEs will be documented from the time of informed consent until the time screen failure is documented, or until the subject is either discontinued from the study or all Week 24 study assessments have been completed and should be followed until either resolution (or return to normal or baseline values), until they are judged by the Investigator to no longer be clinically significant, or for at least 30 days if the AE extends beyond the final study visit.
- ^q Detailed prostacyclin-related AE collection will occur during the inpatient transition phase.
- ^r A pre-baseline review form must be completed and submitted for Sponsor approval after all screening assessments have been conducted for permission to move forward with the Baseline visit assessments.

			Treatment ^e				
Study Visit/Week	Screening ^a	Baseline ^a	Week 3 ^b	Week 6 ^b	Week 12 ^b	Week 24 ^b / Premature Termination ^c	
Study Day	-28 to -1	0/1	22	43	85	169	
Informed Consent	Х						
Inclusion/Exclusion Criteria	X	Х					
Demographics	Х						
PAH History	X						
Medical History	X						
Physical Examination	X					X	
Clinical Laboratory Parameters	X	Х			Х	Х	
Urine Pregnancy Test ^d	X	Х	Х	Х	Х	Х	
PedsQL Questionnaire ^e		Х			Х	Х	
Vital Signs ^f	X	Х	Х	Х	Х	Х	
12-lead ECG		Х				Х	
Cardiac MRI ^g		Х				Х	
PAH Symptoms		Х	Х	Х	Х	Х	
Panama and WHO Functional Classification	Х	Х	Х	X	X	Х	
NT-pro-BNP		\mathbf{X}^{h}			Х	X ^h	
6MWT/Borg Dyspnea Score	Xi	X ⁱ	Xj	Xj	Xj	X ^j	
CPET		X^k				X ^k	
Pharmacokinetic evaluation ¹						Х	
Administration of oral treprostinil		Х					
Dosing Instructions / Dosing Diary		Х	Х	Х	Х		
Drug Accountability / Compliance			Х	X	Х		
Telephone Contact ^m		Х				X	

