7.4 TREATMENT PHASE

The following visits will be conducted in subjects during the 24-week study duration. If the subject is in the hospital during one of the scheduled study visits, the assessments for that visit will be conducted as scheduled during the defined visit window.

7.4.1 Week 0/ Study Days 1-5 (Cohort 1 Only: IV/SC Remodulin to Oral Treprostinil Transition)

The subject will be admitted to the hospital prior to initiating the transition from IV/SC Remodulin to oral treprostinil. Day 1 signifies the day of the first dose of oral treprostinil. For each day (Days 2-5) of the hospital stay, the following assessments will take place:

- Vital signs (following at least five minutes of rest; collected prior to 6MWT or at least 30 minutes following 6MWT)
- PAH symptoms
- 6MWT/Borg dyspnea score (should occur within 2-6 hours of the subject's last dose of oral treprostinil),includes oximetry and HR recovery monitoring (to be conducted following at least five minutes of rest); Borg dyspnea score to be conducted immediately following 6MWT)
- Dose adjustments of oral treprostinil and IV/SC Remodulin (TID or QID, as appropriate)
- Adverse events (including daily administration of a detailed prostacyclin-related adverse events questionnaire)
- Concomitant medications

If the subject stays in the hospital longer than five days, these assessments do not need to be collected on the days beyond Day 5; with the exception of dose adjustments, collection of AEs and changes in concomitant medications which must be collected for the duration of the hospital stay. Following discharge from the hospital, subjects/caregivers will be contacted daily (excluding weekends) via telephone or email by a member of the study team for the first two weeks of the study.

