15.3 PEDIATRIC QUALITY OF LIFE INVENTORY (PEDSQL)

15.4 GUIDELINES AND DEFINITIONS FOR RECORDING ADVERSE EVENTS

The Principal Investigator or a designated member of his/her staff will probe each subject for any AEs that may have occurred. The Investigator should always ask the same question when conducting the verbal probe in order to ensure uniformity between subjects. The Investigator should ask:

"How are you doing (feeling)?"

Based on the subject's response to this question, the Investigator should ask additional questions relevant to the specific complaint such as:

"How severe is/was the symptom?"

"How often did the symptom occur?"

"How long did the symptom last?"

It is the Investigator's responsibility to review the results of all diagnostic and laboratory tests as they become available and ascertain if there is a clinically significant change from baseline. If the results are determined to be a clinically significant change from baseline, this should be reported as an AE. The Investigator may repeat the diagnostic procedure or laboratory test or request additional tests to verify the results of the original tests. When possible, a diagnosis associated with the abnormality should be used as the reported AE.

Using provided definitions, the Investigator will then:

- (1) rate the intensity and seriousness of the AE,
- (2) estimate the causality of the AE to oral treprostinil (study drug), and
- (3) note actions taken to counteract the AE.

Definitions of Intensity, Seriousness, Causality, Action Taken, and Outcome

INTENSITY

An assessment of the relative intensity (severity) of an AE is based on the Investigator's clinical judgment. The maximum intensity encountered during the evaluation period should be checked. The assessment of intensity should be independent of the assessment of the seriousness of the AE.

SERIOUSNESS

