### 11.3 ADVERSE EVENTS

The AEs are collected from the time the informed consent form is signed until study termination. There are a number of AEs that are considered expected events given the underlying disease of study, PAH. These expected events attributable to PAH were not

recorded as an AE unless the event was serious or unusual with respect to intensity, frequency, or duration, or there was a reasonable possibility that it may have been caused by the study drug.

Adverse events will be coded using MedDRA PTs and SOC. All AEs reported in the eCRF will be listed, including non-treatment-emergent and treatment-emergent events.

Non-treatment-emergent AEs are defined as those AEs starting prior to the date of first oral treprostinil dosing. Treatment-emergent adverse events (TEAEs) are defined as those AEs starting on or after the date of first oral treprostinil dosing. The listing will include cohort, subject number, verbatim term, PT, SOC, treatment-emergent status, start/stop date, seriousness, severity, frequency, relationship to oral treprostinil, action taken with oral treprostinil, relationship to background medication, action taken with background medication, and outcome.

The TEAEs will be summarized first in an overall summary, which includes the number of subjects with at least 1 TEAE, at least 1 oral treprostinil attributable TEAE, at least 1 serious TEAE, at least 1 TEAE leading to oral treprostinil discontinuation, at least one background therapy attributable TEAE, at least one TEAE leading to background therapy discontinuation, and any fatal TEAEs. The overall summaries will also include the number of events for each of these categories.

Non-treatment-emergent AEs will be summarized by cohort using PTs. The PTs will be sorted by decreasing overall frequency.

The TEAEs and serious TEAEs will be summarized by cohort using SOC/PT and PT, separately. The summaries will include the number and percentage of subjects reporting and the number of events reported for each SOC/PT and each PT, respectively, for each cohort, in order of decreasing overall frequency, both within SOC and PT.

The TEAEs will be summarized by severity within PT. The TEAEs and serious TEAEs considered attributable to oral treprostinil will be summarized by SOC/PT and PT, as

described above. The TEAEs leading to oral treprostinil discontinuation will be summarized by PT.

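### A structured prostacyclin-AE diary used only during the Cohort 1 hospital stay may raise that cohort's prostacyclin-type TEAE rates, and the SAP neither tabulates the diary nor identifies the affected events

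*Protocol*

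**What the plan says.** **Cohort 1.** Protocol 3.3.2.5 provides that "a detailed collection of prostacyclin-related AEs will be captured via a standardized diary completed by the subject and/or caregiver each day". The sentence then limits the period: "each day of the five day inpatient hospital stay during the transition from IV/SC Remodulin to oral treprostinil or all subjects in Cohort 1". (The conjunction before the last phrase looks like a misprint; the other two places confine the instrument to the Cohort 1 hospital stay.) A footnote to Table 3-1 in Section 3.2 agrees: "Detailed prostacyclin-related AE collection will occur during the inpatient transition phase". Section 7.4.1 places the collection under the adverse-event item, "including daily administration of a detailed prostacyclin-related adverse events questionnaire", but introduces the list with "For each day (Days 2-5) of the hospital stay, the following assessments will take place".

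**Cohorts 2 and 3.** Table 3-2 has no matching footnote. In every cohort, subjects or caregivers are asked directly about AEs at visits and at the mandatory calls (3.3.2.5). Calls are made every weekday for the first two weeks, and email may replace them (3.3.2.6). The general probe is a single open question, and Appendix 15.4 explains why it is fixed: "The Investigator should always ask the same question when conducting the verbal probe in order to ensure uniformity between subjects".

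**SAP.** Section 11.3 states: "The TEAEs and serious TEAEs will be summarized by cohort using SOC/PT and PT, separately". Terms are ordered by overall frequency. The AE listing includes start and stop dates but no source of report. Sections 13.1 to 13.3 name no table, listing or figure for the diary.

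**The concern.** Safety and tolerability is the primary objective, and the TEAE tables are its main descriptive output. A standardized instrument aimed at prostacyclin effects will tend to pick up headache, flushing, nausea or jaw pain that an open question may miss. Cohort 1 has that instrument during its inpatient transition; the other cohorts do not have it at any time.

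The tables count each subject once per term, so a single diary entry that becomes an AE makes that child a case for the whole 24 weeks. A higher Cohort 1 rate could then partly reflect how the events were collected. The overall frequency used to order the tables mixes two methods of collection. A reader of the tables could not tell which events are affected, and the structured record of tolerability during the switch would have no summary of its own.

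**Working it through.** The plan states no figure on this point, so there is none to reproduce. The check compares the sections and then sizes the possible effect.

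**1. How long the diary runs.** Treatment lasts 24 × 7 = 168 days. Five days is 5/168 = 3.0%. Under the Days 2–5 wording of Protocol 7.4.1 it is 4/168 = 2.4%.

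**2. What Cohorts 2 and 3 have in the same period.** With weekday contact, Days 1–5 contain 3 to 5 contacts depending on the weekday of the first dose. Days 1–14 always contain 10. The contrast is therefore mainly a structured instrument against an open question, and only partly a matter of frequency.

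**3. Whether diary entries become AEs.** Section 3.3.2.5 calls the content AEs, and 7.4.1 files the questionnaire under adverse events, so transcription is implied. No rule is given. The rule matters because nausea is named as a characteristic prostacyclin effect in Protocol 1.2.4 and also appears in Table 9-1 as an expected PAH event, which is not recorded as an AE unless certain conditions hold.

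**4. Whether the SAP handles it.** Among the daily inpatient assessments in 7.4.1, these have their own Week 0 tables for Cohort 1:
- walk distance (14.2.3.2) and walk recovery (14.2.3.5)
- Borg score (14.2.4.1)
- PAH symptoms (14.2.5.1)
- vital signs (14.3.4.1)

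The prostacyclin-AE collection has none. None of the TEAE tables (14.3.1.1 and 14.3.1.3 to 14.3.1.12) is split by source of report or by transition period.

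**5. Possible size (illustration; all inputs assumed).** Let *p* be the true incidence, equal in all cohorts. Let *s* be the chance that open questioning picks up a case at some point in the study, *f* the share of cases with an occurrence on diary days, and let the diary capture every such case. Then
- Cohort 1 observed rate = *p*[*f* + (1 − *f*)*s*]
- Cohorts 2 and 3 observed rate = *p s*
- artefactual gap = *p f*(1 − *s*)

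With *f* = 1, the largest case:

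| *p* | *s* = 60% | *s* = 75% | *s* = 90% |
|---|---|---|---|
| 30% | 12 points | 7.5 points | 3 points |
| 50% | 20 points | 12.5 points | 5 points |
| 80% | 32 points | 20 points | 8 points |

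The gap shrinks in proportion to *f*. It is zero if no diary entry is recorded as an AE, or if open questioning would have found every case anyway.

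**6. Precision for scale.** Section 10.2 plans 10–15 subjects per cohort. Exact 95% confidence intervals are 19%–81% for 5/10 and 27%–79% for 8/15.

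**The case against.** The strongest reply is that this is a small feature of a descriptive, non-randomized study. Much of that reply stands, and it rules out four stronger conclusions that a reader might draw.

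- **That Cohort 1 is actively questioned and the others are not.** The diary is confined to about five days, and all cohorts are asked directly about AEs, on weekdays for the first two weeks.
- **That the diary makes the cohorts' rates impossible to compare.** Protocol 10.3.3 plans no inferential safety analysis. The cohorts already differ in prior prostacyclin exposure and in early dose: the three-times-daily Cohort 1 example reaches 5.5 mg on Day 4, while Cohorts 2 and 3 start at 0.125 mg. The diary is one contributor among several.
- **That the diary data will go unreported.** Protocol 10.1 has all assessment results transcribed to the eCRF, SAP 5 puts eCRF data in the locked database, and SAP 8 lists everything in it. What is missing is a named output and a conversion rule.
- **That the diary breaches Appendix 15.4.** That rule governs the verbal probe. The diary is an addition to it.

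It is also fair to say that any figure for the bias is assumed, and that sampling error at 10–15 per cohort is larger than most of the gaps above.

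The reply does not remove the point. Small samples do not cancel a bias with a known direction. The inpatient days are also when Cohort 1 doses change fastest, so a real early excess and a collection effect would fall in the same days and could not be separated in the planned tables.

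**Conclusion.** The point holds as a moderate one. Structured collection of prostacyclin AEs is limited to Cohort 1 during the inpatient transition. The SAP puts the resulting events, unmarked, into common by-cohort tables and gives the diary no table of its own.

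If entries are recorded as AEs, the direction is toward higher Cohort 1 rates of prostacyclin-type TEAEs. The size cannot be derived from the documents: 3 to 32 points is the span over the assumed inputs, with full diary capture and every case showing on a diary day, so smaller values are likely where those assumptions fail. If entries are not recorded as AEs, the TEAE tables are unaffected, and what remains is that the structured data on the switch have no planned summary beyond, at most, a general listing. Other event types, and events that start after the inpatient days, are not directly affected.

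**What to change.** 1. In SAP 11.3 and 13.1–13.2, add a Week 0 table and listing of diary symptoms for Cohort 1: subjects with each symptom by day, and worst severity if the diary records it.
2. Present Cohort 1 prostacyclin-type TEAEs split by onset in the inpatient days or later, using the AE start date already collected. If source of report is recorded, rates with and without events known only from the diary are an alternative.
3. Footnote the by-cohort TEAE tables on the difference in collection.
4. State how diary entries become AEs on the eCRF.
5. Reconcile Protocol 3.3.2.5 (a diary completed by subject or caregiver on each of five days) with 7.4.1 (a questionnaire administered on Days 2–5).

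The cost is one or two extra tables, a listing and a little programming. The onset split needs no new data. Visits and treatment are unchanged.

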3.3.2.6 Telephone Contact (All Cohorts)

Daily telephone contact (excluding weekends for all subjects and inpatient hospital stay for Cohort 1 subjects) is required for the first two weeks of the study. Weekly telephone contact is required from the Week 3 visit until the Week 12 visit and then at least every other week until the Week 24 visit.

The purpose of the telephone contact is to instruct the subject/caregiver to titrate their dose of oral treprostinil and assess for AEs and concomitant medications. Subject/caregiver may be contacted via email in lieu of a telephone call; however, email should not replace direct follow-up by telephone or in clinic for clinical significant AEs or other emergent issues. All telephone or email contacts (i.e. any dosing instructions, AEs reported and/or medication changes) with the subject must be noted in the source documentation.

Version: Amendment 2_FINAL_01Sep2016

TDE-PH-206

3.3.2.7 Continued Access Plan

Subjects who have completed the Week 24 Visit will be given the option for continued access to oral treprostinil. During the Week 24 Visit, the Investigator should assess each subject's eligibility for the Continued Access Plan.

3.3.3 Pharmacokinetics or Other Special Study

3.3.3.1 Pharmacokinetic Sampling

Pharmacokinetic blood sampling will occur twice for each subject in Cohort 1; once during Baseline while the subject is still receiving IV/SC Remodulin prior to starting oral treprostinil, and again at Week 24 when the subject has reached a stable dose of oral treprostinil. Subjects in Cohort 2 and 3 will undergo PK blood sampling at Week 24 only.

All blood samples should be drawn within a ± 10 minute window from their scheduled time point. Record the time and reason for late blood draws and document hemolyzed samples in the eCRF. Hemolyzed blood samples may be redrawn as able. Pharmacokinetic parameters derived from treprostinil plasma concentration-time data will be determined for each subject.

Appendix 15.5 contains a detailed description for the PK blood collection, processing, storage, and shipment of all samples.

Baseline PK Assessment (Cohort 1 Only):

At Baseline subjects in Cohort 1 will undergo an 8-hour PK assessment while receiving IV/SC Remodulin within seven days prior to the first dose of oral treprostinil. Blood samples will be obtained from each subject at time 0 and the following subsequent time points: 4 and 8 hours after time 0 for a total of three blood samples. During the Baseline phase, time 0 should be at the same time of day that it is estimated the Week 24 morning oral treprostinil dose will occur (i.e., if the subject/caregiver anticipates the first daily dose of oral treprostinil at Week 24 will be administered at 8 AM, time 0 should be 8 AM).

Baseline Time Points	Sample Time of Day	Comment (Cohort 1 subjects only while on IV/SC Remodulin)
Time 0	8:00	Estimated time that the morning dose of oral treprostinil will occur at the Week 24 PK assessment.
4 hours	12:00	All subsequent blood draws should occur within a ± 10 minute
8 hours	16:00	window from their scheduled time point. At Baseline all blood draws should be based off of time 0.

Baseline PK Assessment Sample Timelines:

Week 24 PK Assessment (All Cohorts):

At Week 24 all subjects (all cohorts) will undergo an 8-hour PK assessment while receiving oral treprostinil. No oral treprostinil dose changes are allowed within five days of the Week 24 PK sampling, unless required to protect subject safety. All subjects on a TID dosing regimen will undergo the Week 24 PK assessment based on the first daily dose (morning dose) of oral treprostinil. If a subject is on a QID dosing regimen, the Investigator may conduct the PK assessment based on the first daily dose (morning dose) or the second daily dose (midday dose) at their discretion. The PK assessment dose of oral treprostinil will be taken in the clinic and should occur approximately 8 hours after the prior evening's last oral treprostinil dose for subjects using the morning dose of oral treprostinil should occur approximately 4 to 6 hours after that day's morning dose.

Blood samples will be obtained from each subject at pre-dose (immediately prior [i.e., 10 minutes ±5 minutes] to administration of the PK assessment dose of oral treprostinil) and the following time points: 2, 4, 6, and 8 hours after the PK assessment dose of oral treprostinil (all time points will be based off of the time the PK assessment dose is administered). No other doses of oral treprostinil should be taken during the PK sampling period if the subject is on a TID regimen. The second daily dose of oral treprostinil (midday dose) on a TID regimen will be taken in the clinic and after the final 8-hour PK sample is collected. Subjects on a QID oral treprostinil regimen will take their next daily dose (midday dose or early evening dose [PM #1 dose] based on timing of PK assessment dose) between the 4 and 6 hour time points of the PK sampling (±10 minutes). The PK assessment dose of oral treprostinil must be observed in the clinic by study personnel and taken with food. A

brief description of the food ingested prior to the PK dose of oral treprostinil administration should be recorded in the source and eCRF. Tablets must not be chewed or broken.

Week 24 Time Points	Sample Time of Day	Comment (all cohorts while on oral treprostinil)
Previous evening dose	24:00	The previous evening last dose at the Week 24 PK assessment should be taken approximately 8 hours prior to the next morning oral treprostinil dose.
Pre-dose	7:50	Blood draw should occur 10 minutes ± 5 minutes prior to the morning dose of oral treprostinil.
Morning dose	8:00	The morning dose at the Week 24 PK assessment will be taken in the clinic and should occur approximately 8 hours after the prior evening's last oral treprostinil dose.
2 hours	10:00	At Week 24 all blood draws should be based off of the morning
4 hours	12:00	dose of oral treprostinil. All subsequent blood draws should
6 hours	14:00	point. $a \pm 10$ minute window from their scheduled time
8 hours	16:00	
Midday dose	16:15	The midday dose should be taken in the clinic with food and after the last PK assessment has been completed.

Week 24 TID PK Assessment Sample Timelines:

Week 24 QID PK Assessment Based on	Morning Dose Sample Timeline:
------------------------------------	-------------------------------

Week 24 Time Points	Sample Time of Day	Comment (All cohorts while on oral treprostinil)
Previous evening dose	24:00	The previous evening dose at the Week 24 PK assessment should be taken approximately 8 hours prior to the next morning oral treprostinil dose.
Pre-dose	7:50	Blood draw should occur 10 minutes ± 5 minutes prior to the morning dose of oral treprostinil.
Morning dose	8:00	The morning dose at the Week 24 PK assessment will be taken in the clinic and should occur approximately 8 hours after the prior evening's last oral treprostinil dose.
2 hours	10:00	All blood draws should be based off of the morning dose of
4 hours	12:00	oral treprostinil. All subsequent blood draws should occur within a ± 10 minute window from their scheduled time point.
6 hours	14:00	Subjects on QID dosing should take their second daily dose of oral treprostinil (midday dose) between the 4 and 6 hour time
8 hours	16:00	points of the PK sampling (±10 minutes)

Week 24 Time Points	Sample Time of Day	Comment (all cohorts while on oral treprostinil)
Morning dose	6:00	The morning dose on the day of the Week 24 PK assessment should be taken approximately 4 to 6 hours prior to the midday dose of oral treprostinil.
Pre-dose	9:50	Blood draw should occur 10 minutes ±5 minutes prior to the midday dose of oral treprostinil.
Midday dose	10:00	The midday dose at the Week 24 PK assessment will be taken in the clinic and should occur approximately 4 to 6 hours after that day's morning dose of oral treprostinil.
2 hours	12:00	All blood draws should be based off of the midday dose of oral
4 hours	14:00	treprostinil. All subsequent blood draws should occur within a
6 hours	16:00	Subjects on OID dosing should take their third daily dose of
8 hours	18:00	oral treprostinil (early evening dose [PM #1]) between the 4 and 6 hour time points of the PK sampling (±10 minutes)

Week 24 QID PK Assessment Based on Midday Dose Sample Timeline:

